9.3 EXPLORATORY EFFICACY VARIABLES

Exploratory efficacy variables will include:

- Primary endpoint RR for Phase 1;
- Primary endpoint RR for Phase 2;
- Percentage negative urine samples in Phase 1;
- Percentage negative urine samples in Phase 2;
- Percent of subjects with evidence of no illicit opioid use by time point;
- Cumulative percentage of subjects with evidence of no illicit opioid use after two months of treatment by time point (from Week 9 to Week 25);
- Percent of subjects with no self-reported illicit opioid use by time point;
- Percent of subjects meeting criteria of stability at Week 13;
- Measures of craving: Desire to Use visual analog scale (VAS) and Need to Use VAS;
- Measures of withdrawal: Clinical Opiate Withdrawal Scale (COWS) and Subjective Opiate Withdrawal Scale (SOWS);
- Percent of subjects without evidence of using other drugs of abuse by time point;
- Supplemental BPN use;
- Additional supplemental counseling;
- Measures of morning need to use/desire to use

9.3.1 RESPONSE RATE (RR) FOR PHASE 1

The treatment differences in RR based on the primary responder definition and based on responder for Phase 1 will be analyzed using chi square test. The percentages for each treatment and between treatment percentage differences will be estimated. The 95% confidence intervals of the estimates will be presented using normal approximation.

9.3.2 RESPONSE RATE (RR) FOR PHASE 2

The treatment differences in RR based on the primary responder definition for Phase 2 will be analyzed using chi square test. The percentages for each treatment and between treatment percentage differences will be estimated. The 95% confidence intervals of the estimates will be presented using normal approximation.

9.3.3 PERCENTAGE NEGATIVE URINE SAMPLES IN PHASE 1 (WEEKS 3-13)

The percentages for each treatment and between treatment percentage differences will be estimated for Phase 1. The 95% confidence intervals of the estimated treatment differences, based on a normal approximation, will be presented. In addition, the percentage negative urine samples will be analyzed using a chi square test.

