12.3.2.4. Analysis of Secondary Efficacy Endpoints

Percentage of Urine Samples Negative for Illicit Opioids

This variable will be defined in the manner per EMA's request. This variable will serve as the primary efficacy variable for EMA NDA and will not be applicable for US NDA submission.

Percent negative urine samples will be derived after applying missing value imputation. This variable will be analyzed via an analysis of variance (ANOVA) model with treatment effects. The difference between the two treatments in percent negative urine samples will be obtained from this model and the two-sided 95% confidence interval for the treatment difference will be presented.

An analysis of non-inferiority in the primary efficacy variable between the two treatments arms will be performed using a margin of 11% point.

Non-inferiority will be concluded if the two-sided 95% confidence interval for the difference between the percent negative urine samples (Active- Control) is above -0.11 .

Cumulative Distribution Function (CDF) of Percent Samples that are Negative for Illicit Opioid (Week 5-24)

Percent negative samples from 14 samples (8 weekly assessments obtained from Weeks 6 to 13, plus 3 monthly assessments obtained at Weeks 17, 21, and 25 and plus 3 random samples) will be calculated for each subject. Missing samples will be imputed as positive before the percentage is derived.

The null hypothesis of no difference in the CDF of the percent of urine samples that are negative for illicit opioids over Weeks 5-24 will be tested at the 5% significance level using Wilcoxon Rank-Sum test. The empirical CDF plot will be presented.

Time to Sustained Abstinence of Opioid Use

For the purpose of deriving time to sustained abstinence of opioid use (i.e., no opioid use through the rest of treatment period for at least 2 months), the time will be define as:

- If the sustained abstinence is obtained during the scheduled visit, time is the number of days between randomization day to the scheduled visit day. For example, if first sustained abstinence is obtained at the Week 8 visit, the time would be 56.
- If the first sustained abstinence is obtained during a random test, time is the number of days between randomization day to the day that random sample is obtained (Random Sample Date – Randomization Date).

Definition for evidence of illicit opioid use and rules for missing value imputation will be outlined in the SAP.

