12.3.2.5. Analysis of Exploratory Efficacy Endpoints

The exploratory efficacy endpoints will include RR during weeks on CAM2038 q1w (Phase 1) and during months on CAM2038 q4w (Phase 2). RR for Phase 1 and Phase 2 will be analyzed using chi square test. The percentages of negative urine samples in Phase 1 and Phase 2 will also be analyzed using chi square test. The 95% confidence intervals of the estimates will be presented using normal approximation.

Additionally, the following exploratory efficacy variables will be analyzed:

- Percent of subjects with evidence of no illicit opioid use by time point;
- Cumulative percentage of subjects with evidence of no illicit opioid use by time point;
- Percent of subjects with no self-reported illicit opioid use by time point
- Percent of subjects meeting criteria of stability at Week 13
- Changes from baseline in Desire to Use VAS, Need to Use VAS, COWS and SOWS over time.
- Percent of subjects without evidence of using other drugs of abuse by time point
- Supplemental BPN use
- Additional supplemental counseling
- Measures of morning need to use/desire to use
- Quantity of illicit opioid use

For the exploratory efficacy variables based on the percentages, the percentages, the differences of percentages (based on normal approximation) and 95% confidence intervals of the differences will be presented. Change from baseline variables will be analyzed via Analysis of Covariance (ANCOVA) model with treatment and baseline effects. Treatment effects and treatment differences will be estimated. The two-sided 95% confidence intervals of the between- and within-treatment differences will be presented.

Details of additional measures of efficacy and their analysis will be described prospectively, prior to final database lock and unblinding, in the SAP for this trial.

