4.3 STUDY DESIGN

This is a randomized, double-blind, double-dummy, active-controlled, parallel group multi-center trial, designed to evaluate the non-inferiority of CAM2038 compared to an existing standard of care (SL BPN) in initiation and maintenance treatment with BPN. The trial will involve 4 phases: Screening, Phase 1 (weekly visits), Phase 2 (monthly visits), and Follow-up.

Following Screening and confirmation of eligibility, subjects will be randomized to one of two treatment groups in a 1:1 ratio:

- Group 1: SL BPN tablets + placebo SC injections
- Group 2: CAM2038 SC injections + SL placebo tablets

Following randomization, subjects will undergo initiation of BPN treatment with either SL BPN or SC CAM2038 q1w, and participate in weekly visits for 12 weeks (Phase 1). After Week 12, subjects will be transitioned to Phase 2 with monthly visits. During Phase 2, subjects in Group 1 will continue treatment with monthly dispensing of daily SL BPN treatment and monthly placebo SC injections, and subjects in Group 2 (receiving CAM2038 q1w) will be transferred to monthly injections of CAM2038 q4w and monthly dispensing of daily SL placebo. Subjects will participate in 6 visits during the 12 weeks of Phase 2; 3 scheduled monthly visits and 3 random urine toxicology visits. At each random urine toxicology visit, subject's self-reported illicit use will be collected. After Phase 2, subjects will be followed-up for 4 weeks.

A total of 18 opioid urine toxicology samples will be collected during Phase 1 and Phase 2 of the trial, whereof 12 samples will be collected at the scheduled weekly visits during Phase 1. A total of 6 opioid urine toxicology samples will be collected during the 12 weeks of Phase 2 (3 at the scheduled monthly visits and 3 at random urine toxicology visits). A self-report of drug use will accompany every urine toxicology test.

Subjects who complete the 24 weeks of treatment (i.e., Phase 1 and Phase 2) will be transitioned to standard of care (e.g., SL BPN) and be followed up for 4 weeks.

All subjects will be blinded to their treatment group assignment, as will all trial staff with the exception of the clinician(s)/staff performing the SC injections and designated personnel who will be responsible for drug accountability (i.e., counting the active and placebo SL BPN returned tablets).

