6.0 GENERAL CONVENTIONS

Unless otherwise stated, all analyses will be performed using SAS Version 9.2 or higher and all hypothesis tests will be conducted at a two-sided significance level of 0.05. P-values will be presented with 3 decimals and p-values that are less than 0.001 will be presented as <0.001.

Continuous (non survival related) data will be summarized using descriptive statistics: number of observations (n), mean, standard deviation (SD), median, minimum, and maximum. Frequencies and percentages will be used to summarize categorical (discrete) data. Presentations of categorical data will generally suppress percentages for items where the count is zero in order to draw attention to the nonzero counts. In general, mean, standard deviation, median, minimum, maximum, and percentages will be presented with one decimal.

Unless otherwise stated, confidence intervals, when presented, will be constructed at the two-sided 95% level. For binomial variables, the 95% confidence intervals will be constructed using the normal approximation without continuity correction.

Data listings will present all data collected on case report forms (CRFs) by study drug, center, and subject number. Unless otherwise stated data will be presented by treatment and overall.

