9.1.1 DERIVATION OF RESPONSE RATE

For the purpose of deriving the RR, the following rules will be used:

Time Windows for Illicit Opioid Use Assessment

For easy discussion, unless otherwise stated a window denoted as Week (x+, y) for efficacy assessment is a window that covers a period between Week x +1 day to Week y day (exclusive of Week x day but inclusive of Week y day). A window denoted as Weeks x-y for efficacy assessment is a window that covers a period between Week x day to Week y day (inclusive of Week x day and Week y day).

Subjects will receive 12 weekly injections from Week 1 (Day 1 Week 1) through Week 12. Subjects will then receive three monthly injections at Week 13, Week 17, and Week 21. Since the last weekly dosing will occur at Week 12, the efficacy assessments collected at Week 13 reflected effects of weekly dosing in Phase 1. The Phase 1 window is Week (1+, 13). Since the last monthly dosing will occur at Week 21 Phase 2 efficacy window will be Week (13+, 25).

Due to visit date deviation, the actual days in Phase 1 and Phase 2 may not be exactly equal to 91 days (13 weeks) and 84 days (12 weeks), respectively. Similarly, for analysis purpose, weekly and monthly windows will be based on the visit windows, instead of exact 7-day and exact 30-day windows.

Evidence of Illicit Opioid Use within a Window

Subject response for Phase 1 will be based on the 12 scheduled weekly post-baseline urine samples collected from Weeks 2-13. Subject response for Phase 2 will be based on the 3 scheduled monthly urine samples collected at Weeks 17, 21, and Week 25 and the 3 random samples. Evidence of illicit opioid use within a window is defined as a positive opioid urine toxicology result or self-reported illicit opioid use within that window, including the results from random urine toxicology samples (in Phase 2) obtained within that window. Therefore, there is evidence of illicit opioid use, if self-reported illicit opioid use is present, regardless of the opioid urine toxicology result is positive or negative.

If urine toxicology samples are missing, for example, due to missing scheduled visit, early discontinuation of the study, or subject's refusal to provide the samples (scheduled or random samples), the results will be imputed as positive according to the Missing Value Imputation rules discussed in Section 9.1.3 of the SAP.

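### Chi-square tests of percent negative urine samples in Phase 1 and Phase 2 ignore repeated samples per subject, so their p-values and natural-reading intervals are invalid

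*SAP*

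**What the plan says.** SAP 9.3.3 estimates the Phase 1 percentage of negative urine samples in each arm and the difference between arms. For the interval it states: "The 95% confidence intervals of the estimated treatment differences, based on a normal approximation, will be presented". For the test it states: "In addition, the percentage negative urine samples will be analyzed using a chi square test". SAP 9.3.4 repeats this for Phase 2. Protocol 12.3.2.5 agrees: "The percentages of negative urine samples in Phase 1 and Phase 2 will also be analyzed using chi square test".

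None of these sections names the unit of analysis or mentions correlation between samples from one subject. The general rule in SAP 6.0 has no clustering term: "For binomial variables, the 95% confidence intervals will be constructed using the normal approximation without continuity correction".

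Each subject contributes many samples. For Phase 1, SAP 9.1.1 says: "Subject response for Phase 1 will be based on the 12 scheduled weekly post-baseline urine samples collected from Weeks 2-13". The heading of SAP 9.3.3 says Weeks 3-13, which would be 11 samples. For Phase 2, SAP 4.3 says: "A total of 6 opioid urine toxicology samples will be collected during the 12 weeks of Phase 2". SAP 9.1.3 counts every missing sample as positive.

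Elsewhere the plan treats this type of variable differently. For overall percent negative samples, protocol 12.3.2.4 says: "This variable will be analyzed via an analysis of variance (ANOVA) model with treatment effects". SAP 9.2.1 computes a percentage for each subject over Weeks 5-25 and uses a Wilcoxon rank-sum test.

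**The concern.** A chi-square comparison of proportions needs counts of independent units. There are two ways to read the plan:

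- **Samples are pooled.** Each arm then contributes about 190 × 12 = 2,280 Phase 1 results from only 190 people, and they are analysed as if independent. Results from one person are correlated, and the missing-as-positive rule adds runs of identical results for every dropout.
- **One percentage per subject.** The outcome is then not a yes/no count, and a chi-square test of proportions does not apply.

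The wording closely matches the retention-rate text in SAP 9.2.3. There the test is sound, because each subject gives one yes/no result.

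Phase 1 covers the weekly product and Phase 2 the monthly product. A false difference, in either direction, could therefore be read as a finding about one formulation.

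**Working it through.** **Inputs.**

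- 190 subjects per arm, and an SD of 30 percentage points for percent negative samples (protocol 12.5).
- m = 12 samples per subject in Phase 1 (SAP 9.1.1), or 11 by the SAP 9.3.3 heading; 6 in Phase 2; 18 in total (SAP 4.3).
- Two-sided 5% level (SAP 6.0).
- The documents do not give the negative rate expected in this trial. I use 35.1%, the historical SL BPN figure in protocol 12.5, and then an assumed range of 20% to 70%.

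**1. Reproduce the plan's own figure.** Protocol 12.5 states over 90% power for non-inferiority on overall percent negative samples, with a margin of 11 points.

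Power = Φ(11 / (30 × √(2/190)) − 1.96) = Φ(3.57 − 1.96) = 94.7%, which agrees.

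This calculation uses 190 subjects as the sample size, so the 30 points is a between-subject SD. The historical interval of 11.5% to 29.9% (119 and 54 subjects) gives a similar value: (9.2/1.96) / √(1/119 + 1/54) = 28.6 points.

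**2. Correlation implied by that SD.** At p = 0.351, independent samples would give a variance of p(1−p)/18 = 0.2278/18 = 0.01266 for one subject's proportion.

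- Design effect over 18 samples = 0.30² / 0.01266 = 7.11
- ICC = (7.11 − 1)/17 = 0.36

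**3. Apply it to each phase.** I assume that the ICC from the 24-week variable holds within each phase.

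- Design effect: D = 1 + (m − 1) × ICC
- Pooled half-width: 1.96 × √(2p(1−p)/(190m))
- Correct half-width: pooled half-width × √D
- True type I error: 2 × (1 − Φ(1.96/√D))

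For m = 12: D = 1 + 11 × 0.3595 = 4.95 and √D = 2.23. The pooled half-width is 1.96 × √(2 × 0.2278/2280) = 2.8 points, and the correct one is 6.2 points. Type I error is 2 × (1 − Φ(0.88)) = 38%.

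| Phase and m | D | Pooled half-width | Correct half-width | Ratio | Type I error | Coverage of the 95% interval |
|---|---|---|---|---|---|---|
| Phase 1, 12 | 4.95 | 2.8 | 6.2 | 2.23 | 38% | 62% |
| Phase 1, 11 | 4.60 | 2.9 | 6.2 | 2.14 | 36% | 64% |
| Phase 2, 6 | 2.80 | 3.9 | 6.6 | 1.67 | 24% | 76% |

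Half-widths are in percentage points. A beta-binomial simulation of 20,000 trials with identical arms gave chi-square rejection rates of 38.1%, 36.1% and 24.4%.

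**4. Sensitivity.**

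- *Negative rate from 20% to 70%.* The implied ICC is 0.32 to 0.54. The width ratio is 2.1 to 2.6 in Phase 1 and 1.6 to 1.9 in Phase 2. Type I error is 34% to 46% and 23% to 31%.
- *SD of 30 points applied directly to each phase.* The correct half-width is 1.96 × 30 × √(2/190) = 6.0 points. The ratio is 2.0 to 2.6 in Phase 1 and 1.5 to 1.8 in Phase 2.
- *ICC assumed freely, at 0.1 / 0.3 / 0.5 / 0.7.* Type I error is 18% / 34% / 44% / 51% in Phase 1 (m = 12) and 11% / 22% / 29% / 36% in Phase 2.

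**The case against.** The strongest reply is that the documents never say samples are pooled. A normal-approximation interval could be built from per-subject percentages and their empirical SD, and it would then be valid. This is fair as far as it goes. But neither SAP 9.3.3 nor 9.3.4 says so. The chi-square test on the same percentage, read with the binomial rule in SAP 6.0, points to the binomial interval. The test itself fails on either reading.

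Three further points stand and limit the consequence:

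- Both variables are exploratory (SAP 9.3) and absent from the ordered hypotheses in SAP 9.5.
- With every missing sample counted as positive, all subjects have the same denominator. The pooled percentage then equals the mean of the per-subject percentages, so the point estimates are unaffected.
- The phase-specific question does not rest on these analyses alone. SAP 9.3.1 and 9.3.2 compare one responder result per subject in each phase, where a chi-square test is valid. SAP 9.3.5 adds an overall Wei-Lachin test across time points.

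It is also true that the protocol 12.3.2.4 ANOVA belongs to a variable kept for the EMA and not applicable to the US submission. The precedent inside this SAP is the Wilcoxon test of 9.2.1.

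**Conclusion.** The concern holds. The chi-square test in SAP 9.3.3, SAP 9.3.4 and protocol 12.3.2.5 is not valid for a variable with 6 to 12 samples per subject, and the interval on its natural reading is too narrow. With the correlation implied by the protocol's SD, the pooled interval is half the correct width or less in Phase 1, and about 52% to 62% of it in Phase 2. False positive rates are about 34% to 46% and 23% to 31% at a nominal 5%.

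These sizes rest on two assumptions: a negative rate between 20% and 70%, and the 24-week SD carrying over to each phase. The direction does not depend on them. Even an ICC of 0.1 gives 17% to 18% in Phase 1 and 11% in Phase 2.

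The plan should be corrected, but the error does not touch the primary conclusion.

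**What to change.** In SAP 9.3.3 and 9.3.4 and in protocol 12.3.2.5:

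1. Define the variable as each subject's percentage of negative samples in the phase, with missing samples counted as positive.
2. Replace the chi-square test with a per-subject ANOVA on treatment, as in protocol 12.3.2.4, or with the Wilcoxon test of SAP 9.2.1. A GEE logistic model clustered on subject is an acceptable alternative.
3. Report the difference in mean percentages with a 95% confidence interval based on between-subject variance.
4. Settle the Phase 1 window in the same edit: Weeks 3-13 in the SAP 9.3.3 heading against Weeks 2-13 in SAP 9.1.1.

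The cost is a change of wording and a few lines of code. No new data are needed. The intervals become wider, which is correct.

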9.3.4 PERCENTAGE NEGATIVE URINE SAMPLES IN PHASE 2 (WEEKS 14-25)

The percentages for each treatment and between treatment percentage differences will be estimated for Phase 2. The 95% confidence intervals of the estimated treatment differences, based on a normal approximation, will be presented. In addition, the percentage negative urine samples will be analyzed using a chi square test.

9.3.5 PERCENT OF SUBJECTS WITH NO ILLICIT OPIOID USE BY TIME POINT

For the purpose of deriving percent of subjects with no illicit opioid use by month, the same definitions for monthly window and evidence of illicit opioid use (see Section 9.1.1) and the same rules for missing value imputation (see Section 9.1.3) will be used in the calculation.

The treatment differences in these by month variables will be analyzed using chi square tests. The percentages for each treatment and between treatment percentage differences will be estimated. The 95% confidence intervals of the estimates will be presented using normal approximation.

The overall treatment difference will be tested via Wei and Lachin procedure. In this analysis, missing values were not imputed.

9.3.6 CUMULATIVE PERCENTAGE OF SUBJECTS WITH EVIDENCE OF NO ILLICIT OPIOID USE BY TIME POINT AFTER 2 MONTHS OF TREATMENT

The cumulative percentage of evidence of no illicit opioid use will be calculated for all post baseline scheduled visits after two months of treatment (from Week 9 to Week 25). The same definition for evidence of illicit opioid use (see Section 9.1.1) and the same rules for missing value imputation (see Section 9.1.3) will be used in the calculation. As the percentage is derived on a cumulative basis, subject will be included in the numerator (i.e., users) at a given scheduled visit, if the subjects have evidence of use at any prior visits or at the current visit.

The cumulative percentages by month will be analyzed using chi square tests. The percentages for each treatment and between treatment percentage differences will be estimated. The 95% confidence intervals of the estimated treatment differences will be presented.

The overall treatment difference will be also tested via Wei and Lachin procedure. In this analysis, missing values were not imputed.

9.3.7 PERCENT OF SUBJECTS WITH NO SELF-REPORTED ILLICIT OPIOID USE BY TIME POINT

Percent of subjects with No Self-Reported Illicit Drug Use by time points (by scheduled post baseline visit) will be analyzed using chi square tests. The percentages for each treatment and between treatment percentage differences will be estimated. The 95% confidence intervals of the estimated treatment differences will be presented.

9.3.8 PERCENT OF SUBJECTS MEETING CRITERIA OF STABILITY BY TIME POINT

At each weekly visit, starting at Week 5, the subjects will be evaluated with regard to the following stability criteria:

- Has the subject been on a stable dose of CAM2038 q1w/Placebo SC injections without any fluctuations in doses for the last 4 weeks?
- Does the subject exhibit minimal subjective and no objective withdrawal symptoms, based on SOWS ≤ 7 and COWS < 5 ?
- Does the subject exhibit diminished desire/need to use, based on VAS scores (defined as at least 50% reduction from baseline in the VAS score)?
- Does the subject exhibit diminished use of illicit opioids, according to the Investigator's discretion?

Percent of subjects meeting criteria of stability by time point (by scheduled post baseline visit) will be analyzed using chi square tests. The Week 13 will be the primary time point. The percentages for each

treatment and between treatment percentage differences will be estimated. The 95% confidence intervals of the estimated treatment differences will be presented. Additionally, for the primary time point (Week 13), sensitivity analysis will be performed quantifying the number of subjects with at least 25% reduction in positive urine test performed at Weeks 10-13 compared to Weeks 2-5.

The overall treatment difference will be also tested via Wei and Lachin procedure.

